9.8. Quality control

9.8.1. Record maintenance and retention

Neither a subject's name nor initials are to appear on documents transmitted to Nordic in order to maintain confidentiality. Additional anonymisation / pseudo-anonymisation laws as applicable by country will also be adhered to.

In order to provide Nordic/ the CRO with accurate, complete, and legible data, the following criteria are to be maintained:

1. Source documents will be completed to support the data that is entered into the eCRF system.
2. eCRF entries should be made as close to the treatment of the subject as possible.

9.8.2. Data monitoring

To ensure the quality of data collected during the study each site will be monitored centrally by review of data collected in the eCRF.

9.8.3. Quality Assurance (QA)

According to local regulation in participating countries, Nordic can undertake any Quality Assurance related activity upon decision of Nordic Quality Assurance department. The decision will be based on the level of risk to the study subject and on any reported/ identified problem.

QA activities may be outsourced to CROs or independent consultants.

A Competent Authority may also wish to conduct an inspection (during the study or after its completion). If an inspection is requested by such Authority, the Investigator must inform Nordic immediately that this request has been made.

According to local regulation in participating countries, the Investigator will make all the study-related source data and records available to a quality assurance auditor mandated by the sponsor, or to domestic or foreign regulatory inspectors.

The Investigator is required to support audit / inspection activities, to be available to the auditors/inspectors upon request and to permit the auditor/inspector direct access to source data/documents.

9.9. Limitations of the research methods

This study is designed to recruit all patients who are exposed to Nordic Aprotinin during routine clinical practice in participating countries in Europe. Recruitment rate of subjects has been estimated based on likely prescription rates.

Owing to differing clinical practice between countries and centres who will recruit subjects into the study protocol, the eCRF template has to be simple and flexible to allow for different assessments conducted.

This is a non-interventional study with its limitations. No control arm is planned to compare the study treatment with other alternatives. The Registry will not allow a direct comparison of mortality and morbidity among patients treated with Nordic Aprotinin to patients not treated with Aprotinin. Mortality and morbidity outcomes vary according to patient selection criteria by centre and by country

of treatment. Historical controls are not wholly reliable as patient selection and operative techniques vary over time. It is proposed to examine external data bases for comparative purposes as these may be used as a yardstick to measure patient outcomes, e.g. reports from existing national or European cardiac surgical databases.

The limitations of this study are common to all registry data collections.

Patients may refuse the use of their personal data for research purposes. The number of refusals will be kept track of. The impact of these patients on the overall results is expected to be negligible due to their low numbers and the a priori small relationship with the variables of interest.

Entry of patients may be incomplete. It will be mandatory for centres to confirm their willingness to participate in the registry in order to receive supplies of the product. The completion of the Registry for all points of information is not mandatory. In order to ensure the maximum return of individual data key pages have been included which are mandatory.

Nordic will actively follow-up all centres to ensure that Key Data are being entered. This will be performed by comparing sales figures and Registry data (number of patients included and doses used). If it is found that some patients have not been entered into the registry the company will contact the centre concerned to ensure that minimal Key Data are collected and that future patients enter the Registry.

The potential limitation induced by missing data due to incompleteness or absence of any data will be assessed through the number of missing data for each variable of key interest and the breakdown by cause of missing information provided by the data manager (see imputation of missing data).

Data are entered in some hospitals by the same person treating the patients, which may increase the risk of social desirability bias (e.g. respondents report what they think is expected to happen, rather than what they actually do). However, in most hospitals, data will be entered by a CRA or a healthcare professional responsible for data entry (under supervision of a physician) or another physician. During visits to cardiac surgery centres and trainings, Nordic (or its representatives) will advise to have different persons treating the patients and entering data. Furthermore, the requested information that needs to be entered into the Registry are factual data, therefore limiting interpretation bias.

The prospective design of the study does not allow evaluating the changes in physicians' behaviour before and after the implementation of the new recommendations. Furthermore, the participation of prescribers as investigators of the study may change their own clinical practice, taking into account that this study will be prospective. This "Hawthorne effect" could bias the results but is common to any clinical trial or registry. As the Hawthorne Effect relates to individual behaviour in response to change, it can be assumed that the healthcare professionals concerned in the Registry are indeed likely to change their behaviour. In fact this is an advantage of the Registry and one reason for it being prospective. **It is important for clinicians to adopt the risk minimisation measures, and the Registry will ensure the risk minimisation measures (and relating results) to be read and implemented multiple times** (i.e. every time a patient is entered in the Registry). Once these measures are adopted they should certainly be a part of the team protocols and so will not disappear when the Registry closes.

Primary objectives are updated to fulfil the current definition of a non-interventional study as per Directive 2001/20/EC Art 2(c). Nordic will promote the prescription of the product in accordance with the terms of the marketing authorisation. Nordic does not plan to evaluate efficacy of off-label use.

However, as required by the CHMP, Nordic Aprotinin Patient Registry has to collect information on *“the number of patients who receive aprotinin and indication for administration”*, especially regarding off label use that *“should be assessed as part of the missing information”*.¹

Nordic considers that the best way to ensure that all patients are entered in the Registry and to comply with the CHMP requirement is to conduct data collection prospectively. This was confirmed by experts in the field.

If this prospective data collection regarding off-label use is not possible because e.g. from a national legal point of view, this will be discussed with the national concerned authority prior to launch and data collection in a completely retrospective way based on chart reviews or alternative retrospective approaches would be considered (such approach is likely to lead to loss of data, cf. limitations).

As mentioned above, a prospective design may lead to limitations. However a retrospective design will lead to loss of data: not all cardiac surgery centres have a detailed database that would allow retrospective data collection. Furthermore those databases do not follow all Key Data of the Nordic Aprotinin Patient Registry that have been defined in accordance with the requirements of the CHMP and in line with the approved RMP (e.g. heparinisation monitoring data, use of a test dose, prior exposure to aprotinin...). A mixed prospective/retrospective approach may also lead to confusion of healthcare professionals, and this is likely to lead to reluctance to enrol in the Registry.

One limitation of the NAPaR is the detection of rare events ($\geq 1/10,000$ to $<1/1,000$). In order to detect such outcomes with 95% precision, the sample size included in the NAPaR should be of 29,956 patients.

Frequency	Precision	Sample size
10/100	95,00%	28
1/100	95,00%	298
1/1,000	95,00%	2,994
1/10,000	95,00%	29,956

Therefore, even the initial design of the NAPaR (12,000 patients) could not allow the collection of data regarding such rare events.

An alternative channel of collection, associated with monitoring, should be favored. The MAH suggests using EudraVigilance Data Analysis System (EVDAS) for better evaluation of side effects of aprotinin.

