----------------------------	---	---	---

	
The Investigator will make all the study-related source data and records available to a quality assurance auditor mandated by the sponsor, or to domestic or foreign regulatory inspectors.
 
The Investigator is required to support audit / inspection activities, to be available to the auditors/inspectors upon request and to permit the auditor/inspector direct access to source data/documents.
	
sponsor, or to domestic or foreign regulatory inspectors.
 
The Investigator is required to support audit / inspection activities, to be available to the auditors/inspectors upon request and to permit the auditor/inspector direct access to source data/documents.
	

9.9 Limitation of the research methods
	
9.9. Limitations of the research methods
 
.....
 
When incomplete data will not be recovered the data manager will try to get the cause (fortuitous omission, not pertinent data due to death or other reason, lack of time...) and a field in the database will be filled by the data manager concerning the cause.
	
9.9. Limitations of the research methods
 
.....
 
When incomplete data will not be recovered the data manager will try to get the cause (fortuitous omission, not pertinent data due to death or other reason, lack of time...) and a field in the database will be filled by the data manager concerning the cause.
	
This sentence was deleted because the NAPaR database do not allow the justification of missing or incomplete data. There is no direct communication between the study datamanager and the participating sites.
 
However, the NAPaR data entry completeness is centrally followed, per country and per site, in order to limit the missing data.
 
For now, the targeted rate of complete key data above 80% has been achieved with the concurrence of Medical Science Liaison (MSL) and/or local coordinator.

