9.3.7. Post-operative*

Reoperation if required with reason for re-operation;

The occurrence of post-operative stroke, post-operative myocardial infarction, other post-operative embolic or thrombotic event, and new post-operative dialysis and relative date;

Post-operative serum creatinine level;

Time to recover renal function baseline value, if available;

Any post-operative use of an aminoglycoside antibiotic;

The occurrence of multisystem failure;

Post-operative blood loss;

Status at discharge and if dead the primary cause of death before discharge;

Date of discharge (and post-operative stay).

Note: the average time-to-events for the abovementioned post-operative events are considered the following: less than one day for reoperation for bleeding (Karthik 2004), one day for renal failure (Rosner 2006), 3 days for stroke (Schwann 2007, Hogue 1999, Dafer 2006), 3 days for myocardial infarction (Thygesen 2007), and 6 days for deep vein thrombosis (Hogue 2006). All abovementioned post-operative events have to be collected at any time, even if those occur after the average time-to-events as published in the literature.

The non-key pages are the following:

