As a matter of fact imputation of data is more or less invention of data that can strongly bias results in an observational study. The less speculative approach is therefore to remove from the data patients without the needed information from the analysis.

In data modelling or if a breakdown of the sample is done according a given variable, a missing data in any qualitative covariate (or factor of segmentation of the sample) can have a category called "unknown". A first model will fitted with such a categorization and a second one will be fitted after removing all patients with missing data on the covariate. If it concerns a breakdown of the sample then descriptive statistics along with 95% confidence interval will be provided for all categories including the unknown class. Regarding quantitative covariate, categorization of the covariate may be done and a first model will be fitted with only categorical variables including the "unknown" category and a

second model is fitted with quantitative covariate (patients with a missing data are excluded). Concerning the breakdown the same categorization approach will be applied and estimation will be provided for each category. If a breakdown of the sample is applied the estimation for the "unknown" category will be compared to all the other categories combined to assess whether missing data represent approximately the average of the collected data.

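### Section 9.9 promises a breakdown of missing data by cause that the registry cannot produce, and no planned table shows how many in-hospital deaths drop out of the creatinine-based renal rate

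*Protocol*

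**What the plan says.** Three places in the protocol bear on this.

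- **Section 9.9 (Limitations).** The damage from missing data is to be assessed in two ways: the number of missing values for each key variable, and "the breakdown by cause of missing information provided by the data manager (see imputation of missing data".
- **Section 5 (Amendments and updates), reason given for the change to 9.9.** A sentence was removed that had the data manager seek the cause of each unrecovered blank and enter it in a database field. Its examples of causes were "fortuitous omission, not pertinent data due to death or other reason, lack of time". The reason for removal is that "the NAPaR database do not allow the justification of missing or incomplete data", and that "There is no direct communication between the study datamanager and the participating sites".
- **Section 9.7 (Missing data).** Imputation is rejected: "The less speculative approach is therefore to remove from the data patients without the needed information from the analysis". For covariates and breakdown factors an unknown category may be used. Its estimate is to be "compared to all the other categories combined to assess whether missing data represent approximately the average of the collected data".

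Renal dysfunction, defined by a rise in creatinine from before to after surgery, appears under primary objectives 2 and 3 (section 8.2). Section 9.3.7 lists post-operative creatinine as Key Data, and also "Status at discharge and if dead the primary cause of death before discharge".

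**The concern.** Section 9.9 offers the breakdown by cause as one of two checks on missing-data bias. When the step that would have supplied the causes was removed, the sentence that relies on it stayed. A regulator reading 9.9 would expect a table that nobody can make.

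The check matters because the analysis rule in 9.7 does not look at the reason for a blank. A patient who died in hospital with no post-operative creatinine recorded is removed from the creatinine analysis in the same way as a patient whose value was not entered. The first kind of blank may well be related to the outcome. If so, the renal dysfunction rate describes patients who were measured rather than all patients exposed, and an exact confidence interval does not reveal the difference. The aminoglycoside figure under objective 3 depends on the same renal classification.

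**Working it through.** **Step 1. Can the causes come from anywhere?** Sections 9.6 to 9.9 as they now stand describe entry checks, completeness monitoring, central review of the eCRF and comparison with sales figures. None asks for or stores a reason for a blank. The cross-reference in 9.9 matches no section title. The nearest text, on missing data in 9.7, opens by rejecting imputation and has no cause variable. Section 5 states as a fact about the present database that causes cannot be recorded. So the count per variable is feasible and the breakdown by cause is not.

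**Step 2. What happens to a death without a post-operative creatinine?** Under objective 2 the event is a creatinine rise, with dialysis counted separately. Without the second creatinine the patient cannot be classified, and 9.7 removes them. Under objective 3 dialysis also qualifies, so a patient who died after new dialysis can still count as an event. The unknown category in 9.7 serves covariates and breakdown factors and is a single class not split by reason.

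**Step 3. The plan's own figures, for scale.** With p = 50% and half-width 1.56%, n = 1.96² × 0.25 / 0.0156² ≈ 3,946.3, rounded up to 3,947. The protocol gives 3,951, at which the half-width is 1.559%. Inflation: 3,951 / 0.75 = 5,268. These figures are sound and the point does not depend on them.

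**Step 4. Size, under stated assumptions.** Let m be the share of patients who died before discharge with no post-operative creatinine, and p the complete-case renal rate. Neither is in the documents. Counting these patients as unaffected gives p(1 − m). Counting all as affected gives p(1 − m) + m.

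| p (assumed) | m (assumed) | Patients of 3,951 | None affected | All affected |
|---|---|---|---|---|
| 20% | 1% | 40 | 0.20 × 0.99 = 19.8% | 19.8 + 1 = 20.8% |
| 20% | 3% | 119 | 0.20 × 0.97 = 19.4% | 19.4 + 3 = 22.4% |
| 10% | 1% | 40 | 0.10 × 0.99 = 9.9% | 9.9 + 1 = 10.9% |
| 10% | 3% | 119 | 0.10 × 0.97 = 9.7% | 9.7 + 3 = 12.7% |

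Sampling half-width at N = 3,951: 1.96 × √(0.20 × 0.80 / 3,951) = 1.25 points at 20%, and 1.96 × √(0.10 × 0.90 / 3,951) = 0.94 points at 10%.

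The largest upward shift is m(1 − p). It exceeds the sampling half-width once m passes 1.25 / 0.80 ≈ 1.6% (about 62 patients) at p = 20%, or 0.94 / 0.90 ≈ 1.0% (about 41 patients) at p = 10%.

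**The case against.** The strongest reply is that the clause in 9.9 is a leftover that needs only an editorial correction, and that denominators and bounds belong in the SAP, which exists but is not shown. Part of this stands: the details of a sensitivity analysis are normally SAP matter. But the promise in 9.9 is the protocol's own, and no SAP can tabulate a reason that was never recorded. The SAP listed in Annex 1 is dated 23 September 2019, before version 2.1 of March 2020. Nor is this merely a difference between the change log and the current text. The log's reason describes what the database can do, and current 9.9 has no source of causes even if the log is ignored.

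A reader might infer more than the documents support:

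- *That losing the cause field is why deaths are removed.* Removal under 9.7 never depended on cause. The field was descriptive only, so these are two separate points.
- *That nothing shows the deaths.* Death is reported in every analysis, renal failure is reported as fatal and non-fatal, and dialysis is counted independently of creatinine. What is absent is the cross-tabulation of missing creatinine with discharge status.
- *That deletion is the only rule.* The unknown category and its comparison with the other categories remain, as does the count per variable.
- *That about 790 patients lack a creatinine.* Section 5 says "the targeted rate of complete key data above 80% has been achieved". Twenty per cent of 3,951 is 790, but that is a ceiling on records with any incomplete key item, not a measure of missing creatinine.
- *That every blank can be sorted into death, refusal or omission from fields already held.* Patients who refuse have no data entered (section 9.2). Section 9.3.7 lists no separate date of death and no creatinine sampling time, so whether death came before the value could be taken cannot be established reliably.

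**Conclusion.** The point holds in two limited parts. First, one of the two missing-data checks in section 9.9 cannot be carried out as written. This follows from the text and needs no assumption. Second, and independently, the cause-blind removal in 9.7 takes in-hospital deaths without a post-operative creatinine out of the creatinine-based renal rate, and the protocol plans no display of their number. The protocol does not say this in so many words; it follows from the rule.

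The size is unknown. On the illustrative assumptions the none/all range is 1 to 3 points wide. At 1% early deaths the largest shift is below the sampling half-width (0.8 against 1.25 points at a 20% rate, 0.9 against 0.94 at 10%). At 3% it is above it (2.4 and 2.7 points), but only if every such patient would have been affected. This is not evidence that the renal rate is biased. It is a reason to show the number, so that a reader can see whether it matters.

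**What to change.** **Section 9.9.** Remove the breakdown-by-cause clause and its cross-reference. Keep the count of missing values per key variable. Add a tabulation of missing key outcome variables, post-operative creatinine in particular, by status at discharge (alive or dead), country and centre.

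**Section 9.7.** Keep the complete-case rate as the main result. Beside the renal dysfunction rate, report the number of patients who died before discharge with no post-operative creatinine recorded, and the rate with these patients counted as none and as all affected. Where the definition in use includes dialysis, count dialysis cases as events first, so that the range applies only to patients still unclassified.

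The category should be worded by what is recorded, namely died before discharge with no value, and not by whether a sample could have been taken. No class for refusals is needed.

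**Cost.** Two short text changes, one extra table and a slightly wider stated range for the renal rate. All fields are Key Data already in the registry, so no new data collection is needed.

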9.10. Other aspects

None.

10. Protection of human subjects

10.1. Declaration of ethical conduct

This study will be conducted in accordance with the standard operating procedures (SOP) of Nordic and the CRO. The study will be conducted according to the following guidelines:

1. Declaration of Helsinki, 1964 (“Recommendations Guiding Physicians in Biomedical Research Involving Human Patients”), and all its accepted amendments to date concerning medical research in humans.
2. Directive 2001/83/EC of the European Parliament and of the Council of 6 November 2001 on the community code relating to medicinal products for human use
3. Regulation (EU) 2016/679 of the European Parliament and of the Council of 27 April 2016 on the protection of natural persons with regard to the processing of personal data and repealing Directive 95/46/EC (General Data Protection Regulation)
4. Guideline on good pharmacovigilance practices (GVP) Module VIII- Post-authorisation safety studies (version in force)

This study will be conducted in accordance with national and local laws of the countries where study sites are located.

The participating physician agrees, when signing the Commitment to participate page, to adhere to the instructions and procedures described in the protocol.

10.2. Ethical, regulatory and other local review

According to local country specific requirements the protocol and associated documentation will be submitted to all relevant local approving bodies. This may include Ethics committees, data protection bodies etc.

Signed letters of positive opinion regarding the study from the relevant local approving bodies must be sent to the Investigator who will provide Nordic/ the CRO with a copy prior to the start of data collection for any subject in the eCRF.

The Registry will comply with local data protection laws.

10.3. The Investigator and associated site staff will collect information according to the protocol

The Investigator and associated site staff must comply with local regulatory laws and regulations concerning post approval safety studies.

